The PI and co-investigators have an existing PCORI-funded project, the PRIMED study, that is examining the impact of training primary care physicians in shared decision making (SDM) on colorectal cancer screening decisions for patients aged 76-85. A PRIMED advisor, [name], is on the task force to determine policies for resuming GI services at MGH and will serve as co-investigator on this study. Together with our stakeholders (including our patient partners and the Colon Cancer Alliance), we have designed two descriptive studies and a randomized controlled trial to examine whether shared decision making will improve colon cancer screening decisions for patients aged 45-75 who have had their colonoscopy delayed due to COVID-19. The findings will not only have direct implications for managing the backlog of colonoscopies, but will also help inform policies for other screening tests and elective procedures.

RESEARCH DESIGN AND METHODS

Briefly describe study design and anticipated enrollment, i.e., number of subjects to be enrolled by researchers study-wide and by Partners researchers. Provide a brief summary of the eligibility criteria (for example, age range, gender, medical condition). Include any local site restrictions, for example, "Enrollment at Partners will be limited to adults although the sponsor's protocol is open to both children and adults."

Across all of the aims, we anticipate enrolling 645 participants study-wide. (Aim 1, n=195 patients completing a survey; Aim 2, n=450 patients completing a survey in the study).

For Aim 1 we will conduct a cross-sectional survey study targeting patients aged 45-75 who had their screening or surveillance colonoscopy postponed or delayed due to the COVID pandemic. We will survey a random subsample of these patients. Table 1 includes information on eligibility for the patient sample. We anticipate inviting 300 patients and estimate receiving 195 completed surveys.

Eligible patients will be sent a survey packet in the mail that will include a cover letter signed by the GI Director of Quality and Safety inviting their participation, an information sheet describing the study, an incentive (\$10), and the survey. The cover letter will include information for participants to opt-out if they desire. Patients will be asked to complete the survey and return it back to study staff. Consent is implied with return of the survey.

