For Aim 2, we will conduct a randomized controlled trial that will enroll patients who have to reschedule colonoscopies. We will randomly assign about 900 patients who are on the waitlist to either intervention or control arm. The intervention arm will receive a shared decision making worksheet that will cover (a) presenting pros and cons of three screening options (first available colonoscopy (wait time estimated to be ~6 months), stool-based test (with consideration that if positive, a follow-up colonoscopy may still be delayed ~3 months), and delay colonoscopy one year); (b) contact information for rescheduling their colonoscopy; and (c) contact information to connect with staff if they have questions or need more information. GI clinicians will be recruited and complete an online SDM training prior to their visit with patients who have more questions and request a GI visit. The control group will receive the standard department guidance and policies on scheduling. We will invite patients to complete a survey to track SDM, decisional conflict, overall anxiety and cancer worry, preference for colonoscopy, concerns about accessing health care-and we will also track any testing received within 6 months. We estimate sending a survey to about 700 patients across both arms and receiving 450 completed surveys.

For Aim 3, we will follow all MGH patients who had their screening or surveillance colonoscopy delayed for 12 months and will document receipt of colonoscopy or other colon cancer screening test, and if they got a colonoscopy, will calculate the wait time for colonoscopy for all of the patients on the waitlist. We will track demographic information, age, gender, race and ethnicity, primary language, zip code. We estimate that there are about 5,000 patients who have had their colonoscopy delayed that will be followed in this chart review portion of the study.

Table 1: Eligibility for patient participants

Eligible	Ineligible

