The intervention mailings went out in four waves, about two weeks apart, between September 10, 2020 and October 22, 2020. Participants in the intervention arm received a decision worksheet in the mail followed by a call from a decision coach. A subset of participants across both arms were selected to receive a survey. Staff mailed a survey to the selected subset of control and intervention participants about 8 weeks after the intervention packet was mailed to their wave. The survey packet included a cover letter, an information sheet, an incentive (\$10 gift card), the survey and a return envelope. Patients were able to complete the survey by mail, online via REDCap, or over the phone with study staff. Staff made up to three reminder phone calls and sent a reminder mailing to non-responders with 3 additional reminder calls. Spanish-speaking research staff conducted reminder calls for Spanish-speaking participants. Staff conducted chart review to collect screening tests completed within 6 months.

Randomization and blinding: The study statistician used a computer random number generator to randomly select 800 eligible patients, assign each to intervention or control arm, and to one of 4 waves. All 800 patients were followed to track colon cancer screening tests completed and a subset in each wave were randomly selected to receive a survey to measure patient-reported outcomes. The staff who entered the data from the paper surveys and who conducted chart review to collect screening were blinded to the assignment. The statistician analyzing the results was not blinded to the assignment.

Outcomes:

Screening uptake: study staff examined medical records to determine receipt of any colorectal cancer screening test for all subjects within 6 months.

The following measures were collected in the patient survey:

SDM Process Scale: 4-item survey asks about discussion of stool test, pros and cons of colonoscopy and patient's screening preference. Total scores range from 0-4 with higher scores indicating higher shared decision making. Patients who indicated that they did not talk with anyone about CRC screening received a SDM Process score of 0.

SURE scale: the brief 4-item version of the decisional conflict scale. A point is given for each "yes" response for total scores 0-4 and we report the percentage receiving the top score of 4, which indicates no decisional conflict.

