Screening preference: One item asked patient's preferred approach to screening (with responses: colonoscopy, stool-based test, delay screening, not sure).

Additional measures were collected to describe the sample and used as covariates including whether or not the patient had a CRC discussion with health care provider in the past two months, PROMIS Scale v1.2-Global Health Physical 2a, Single Item Literacy Screener, CRC screening and history, COVID-19 worry, decision worksheet use and decision coaching exposure. Basic demographics for the full sample were collected via chart review.

Sample Size: The sample size of 800 was determined based on the screening uptake, with 800 participants, the study had 81% power to detect a difference of 10% in rates. For the survey, we assumed a 60% response rate and as a result, planned to invite about 500 patients (250 in each arm) to obtain 300 responses. With 300 survey responses, the study had 80% power to detect a difference of 0.32 standard deviation (SD) for the SDM Process score. Studies have found effect sizes ranging from 0.39SD – 0.88SD for SDM Process when comparing sites that used formal

decision support (coaching or decision aids) and those that did not. For dichotomized survey outcomes (% SURE top score and % prefer screening), with 300 responses, we had 80% power to detect a 13% difference, from 70% to 83%.

Statistical methods: Sample demographics and characteristics were compiled and compared to evaluate the balance between the two arms. Responders and non-responders to the survey were compared between arms to evaluate potential non-response bias.

The following hypotheses were evaluated using an intention to treat approach, and patients were analyzed based on their assigned arm.

1. Compared to the control group, patients in the intervention arm will be more likely to have a screening test within 6 months (the percentage of patients who had either stool test or colonoscopy in each arm compared using a Fisher Exact test). We also used cumulative incidence function to compare time to screening completion.
2. Compared to the control group, patients in intervention arm will report higher SDM scores (compared mean scores using a two sample t-test).

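### The Protocol's Aim 2 sizes (about 900 randomised, 700 surveyed, 450 responses) are not reconciled with the SAP's 800, 500 and 300, and survey precision at 300 needs restating

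*Protocol*

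**What the plan says.** The Protocol (version January 6, 2021), under Research Design and Methods, Aim 2, states: "We will randomly assign about 900 patients who are on the waitlist to either intervention or control arm". On the survey it adds: "We estimate sending a survey to about 700 patients across both arms and receiving 450 completed surveys". The overview at the start of that section says "we anticipate enrolling 645 participants study-wide". The parenthesis after it splits the total into 195 for Aim 1 and, for the trial, "Aim 2, n=450 patients completing a survey in the study".

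The SAP (August 25, 2021), under Randomization and blinding, says that the statistician used random numbers to "randomly select 800 eligible patients, assign each to intervention or control arm, and to one of 4 waves". It continues: "All 800 patients were followed to track colon cancer screening tests completed". Under Sample Size it says "The sample size of 800 was determined based on the screening uptake", and that the study team, assuming a 60% response, "planned to invite about 500 patients (250 in each arm) to obtain 300 responses".

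Only the SAP gives power figures:

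- 81% for a 10-point difference in uptake with 800 patients;
- 80% for 0.32 SD on the SDM Process score with 300 responses;
- 80% for 70% versus 83% on the binary survey outcomes with 300 responses.

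The Protocol gives no power, significance level or detectable difference for Aim 2.

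**The concern.** The documents differ at all three levels of the trial: patients randomised, patients surveyed and surveys returned. The gaps in the survey figures are too large to be rounding. Neither document says that the plan changed, when it changed or why.

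The dates make this harder to pass over. According to the SAP's Design section, the intervention mailings ran from September 10 to October 22, 2020, so patients had been assigned by then. The Protocol version dated eleven weeks later still gives about 900 in the future tense. The only rationale for 800 and 300 stands in a document dated August 2021 and written in the past tense. A reader cannot tell from it whether those sizes were fixed in advance.

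Two things depend on the answer. Hypothesis 1 (uptake) is analysed by intention to treat, which needs an agreed randomised denominator. Hypotheses 2, 3a and 3b rest on the survey, where the expected number of responses is one third lower in the SAP than in the Protocol.

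**Working it through.** **Sizes side by side**

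| | Protocol | SAP | Change |
|---|---|---|---|
| Randomised | about 900 | 800 | −100/900 = −11% |
| Surveyed | about 700 | about 500 | −200/700 = −29% |
| Responses | 450 | 300 | −150/450 = −33% |
| Implied response rate | 450/700 = 64.3% | 300/500 = 60% | |
| Study-wide total | 195+450 = 645 | 195+300 = 495 (not stated in the SAP) | |

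**Assumptions.** Neither document gives a significance level for these calculations, so I take two-sided 0.05. I also assume equal numbers per arm. The SAP gives no control rate for uptake, so I vary it.

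**SDM Process score.** Power = Φ(d·√(n/2) − 1.96), with n per arm.

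- The SAP's own figure, n = 150 and d = 0.32: 0.32 × 8.660 − 1.96 = 0.811, giving 79.1% (78.9% with the t distribution). The stated 80% is reproduced to within rounding.
- The Protocol's 450, n = 225: 0.32 × 10.607 − 1.96 = 1.434, giving 92.4% (t: 92.3%).
- Detectable with 80% power, (1.96 + 0.842)·√(2/n): 0.323 SD at 150 per arm and 0.264 SD at 225 (t: 0.325 and 0.265).

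**Binary survey outcomes, 70% versus 83%.** Power = Φ{[Δ√n − 1.96·√(2p̄(1−p̄))] / √(p₁(1−p₁)+p₂(1−p₂))}, with p̄ = 0.765. The two square roots are 0.5996 and 0.5925.

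- n = 150: (0.13 × 12.247 − 1.1753)/0.5925 = 0.704, giving 75.9%. The stated 80% is not reproduced. Other methods give 76.6% (unpooled variance), 76.4% (arcsine), 72.2% (exact Fisher) and 84.7% (one-sided 0.05).
- 80% power for this contrast needs 332 responses.
- n = 225: (0.13 × 15 − 1.1753)/0.5925 = 1.308, giving 90.4%.
- Detectable rise from 70% with 80% power: 13.6 points at 300 responses and 11.3 points at 450.

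**Screening uptake, 10-point difference.** The same formula applies.

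- 45% versus 55%, n = 400: (0.10 × 20 − 1.3859)/0.7036 = 0.873, giving 80.9%. With n = 450 it gives 85.2%.
- For control rates of 35% to 55%, power is 80.9% to 82.4% with 800 patients and 85.2% to 86.6% with 900. With the planned Fisher test it is 79.3% to 80.3% and 83.4% to 85.4%.
- The stated 81% is therefore reproduced for a mid-range control rate, and moving from 900 to 800 costs about four points.

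**Timing.** October 22, 2020 plus about eight weeks is about December 17, 2020 for the last survey mailing. The Protocol's reminder packet, about four weeks later, falls in mid-January 2021. On January 6, 2021 assignment and the intervention mailings were over, but survey reminders were probably still running.

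**The case against.** The strongest defence is that the two texts differ in kind. The Protocol section answers an ethics-committee prompt about anticipated enrolment, and its figures are forecasts with hedges. The SAP is later and reports conduct. A forecast and a later account may differ, and the SAP is the only document with a sample-size rationale. The SAP also cites earlier effects of 0.39 to 0.88 SD. At 150 per arm, power for 0.39 SD is Φ(0.39 × 8.660 − 1.96) = Φ(1.418), about 92%, so 300 responses are adequate for the SDM comparison on the SAP's own reasoning.

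Much of this stands. It limits the size of the problem and rules out three stronger readings that a reader might infer:

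- **That the documents state conflicting precision.** They do not. The Protocol states none, and the 0.265 SD and 11.3 points are my inference from its 450 responses.
- **That about 100 randomised patients were left out, so the analysis is not intention to treat.** No passage reports that 900 were assigned. The SAP says 800 were selected, assigned and followed, and that patients are analysed in their assigned arm. The CONSORT figure is not shown in the text available here, and its absence is no evidence either way.
- **That the Protocol version postdates all mailings.** It postdates the intervention mailings only.

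The defence does not explain the change. Hedged wording does not cover a move from 700 to 500 or from 450 to 300. A Protocol version dated after assignment should not still forecast a different number to be assigned.

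**Conclusion.** The point holds as an unreconciled and unexplained change of sample size between two documents, neither marked as superseded. The SAP's account makes 800 the likely randomised denominator, but the Protocol does not agree with it.

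The consequence for uptake is small: about 81% power instead of 85% at a mid-range control rate. For the survey it is moderate: a detectable SDM difference of about 0.325 SD where 450 responses would have allowed 0.265 SD, and power at 0.32 SD of 79% instead of 92%. One figure in the SAP changes whatever the Protocol says: 300 responses give about 76% power for 70% versus 83%, not 80%.

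These results rest on two-sided 0.05, equal responders per arm and exactly 300 responses. The uptake figures also depend on a control rate that the SAP does not give.

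**What to change.** 1. In the SAP, confirm that 800 is the number randomised and the intention-to-treat denominator for uptake.
2. In the SAP, add a dated statement of when and why the planned sizes changed from 900/700/450 to 800/500/300, leaving the superseded figures visible.
3. Correct the study-wide total from 645 to 495 (195+300), and bring the Protocol's Aim 2 figures into line by reference to that statement.
4. Restate survey precision for 300 responses, naming the significance level: about 0.325 SD on the SDM score with 80% power, and 13.6 points from 70% for the binary outcomes. Replace the 80% claim for 70% versus 83% with about 76%.

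The cost is wording and a slightly less favourable stated precision. No extra patients are needed and no analysis changes.

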COVID-19 has changed the health care landscape in profound ways in a few short months. Entire hospitals and practices have been refocused to screen for and treat patients with COVID-19. Routine visits, screening tests and elective procedures have been postponed. As the initial surge of patients with COVID-19 recedes, routine care will not simply be able to return to normal. One pressing issue is the large and growing backlog of screening tests and elective procedures at many hospitals. Nationally, data suggest that colonoscopies have dropped 90% since February.ⁱⁱ At Massachusetts General Hospital (MGH) alone, the Gastroenterology (GI) department estimates that about 8,000 colonoscopies have been postponed, more than 5,000 of these are routine screening colonoscopies. Recovery planning programs have been delayed further because of the shortage of PPE and because GI nursing staff have been redeployed to COVID care duties. The department anticipates 2-3 months to ramp up to about 66% of prior volume but does not anticipate getting back to 100% in the next year due to new requirements for infection control that will increase turnover time. To further complicate matters, public health officials warn that multiple waves of infection may occur over the next 12-18 months, and each may cause additional restrictions on capacity, increasing backlogs even more. Managing demand with reduced capacity while planning for additional shutdowns represents a key new challenge for health care systems delivering care during this crisis. Further, even if there is capacity, many patients may feel differently about the value of seeking healthcare, including cancer screening, during the crisis. A recent poll showed that the majority of patients are unlikely to visit a hospital (62%) or specialist (64%), regardless of whether they live in a COVID hotspot.ⁱⁱⁱ There are many challenges to resuming healthcare during this crisis, and important research questions about how to do this in a safe, equitable and patient-centered manner. Some key questions include: How should patients be prioritized for routine screening procedures like colonoscopy? What role should patients' preferences play in the prioritization process? What do health systems need to do to ensure patients are comfortable accessing needed care? How can systems do this without furthering disparities or disadvantaging vulnerable populations?

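### Table 1 lists as ineligible the patients the trial is meant to enroll; separately, the 6-month uptake window matches the estimated colonoscopy wait, and a longer by-arm look would be a cheap addition

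*Protocol*

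**What the plan says.** **Eligibility.** The Aim 2 paragraph of the protocol (Research Design and Methods) describes a trial in people whose colonoscopy still has to be rebooked. In Table 1, the final entry under Ineligible is people who have not yet rebooked or undergone the procedure. The study-procedures text after Table 1 builds the waitlist from three groups: postponed procedures, referrals not yet processed, and patients the department should have contacted but did not. It then has staff check patients against Table 1. The SAP (Design) describes essentially the same three groups for the list extracted on June 2, 2020.

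**Window.** The Aim 2 paragraph gives the first worksheet option as "first available colonoscopy (wait time estimated to be ~6 months" and adds that "we will also track any testing received within 6 months". The SAP defines uptake as "receipt of any colorectal cancer screening test for all subjects within 6 months" (Outcomes). Its first hypothesis is that "patients in the intervention arm will be more likely to have a screening test within 6 months", counting stool test or colonoscopy and using Fisher's exact test. It continues: "We also used cumulative incidence function to compare time to screening completion", with no time horizon given. On sample size it says "the study had 81% power to detect a difference of 10% in rates". The protocol's Background expects a ramp-up over 2-3 months to about 66% of earlier volume, but the department "does not anticipate getting back to 100% in the next year". Aim 3 covers all patients at the hospital who "had their screening or surveillance colonoscopy delayed for 12 months and will document receipt of colonoscopy or other colon cancer screening test". Its comparison, as set out under Specific Aims, is by patient characteristics; trial arm is not named.

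**The concern.** The Table 1 entry is an operative rule, because the protocol directs staff to it for confirming eligibility. A reader or auditor who takes it at its word would conclude that the trial excluded its own target population.

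The window matters for a different reason. A patient who reads the worksheet, chooses colonoscopy and books promptly could, on the protocol's own estimate, be tested at about the moment counting stops. If the arms do not differ at 6 months, two explanations remain: the intervention did not change screening, or it prompted colonoscopies that had not yet taken place. The plan states no by-arm comparison beyond 6 months and no count of procedures pending at that point, so a null result would be harder to interpret than it need be.

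**Working it through.** **1. Table 1 against the rest of the protocol**

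| Patient | Aim 2 text | Table 1 entry as printed | Entry moved to Eligible, or negative removed |
|---|---|---|---|
| Not rebooked, not done | Enrolled | Excluded | Enrolled |
| Already rebooked or done | Not the target | Not excluded by this entry | Excluded |

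The printed entry reverses both rows. The two repairs are logically the same, and either restores agreement. The waitlist definition gives independent support: a patient whose referral was never processed cannot have rebooked, so the printed entry would exclude a group that the waitlist names. The postponed and cancelled groups prove less, because those words do not say whether the procedure was later rebooked.

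**2. The stated power**

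Inputs: 800 patients at 1:1 gives n = 400 per arm, and the difference is 10 points (SAP, Design and Sample Size). The control rate, alpha and sidedness are not stated; I assume two-sided 0.05. With the pooled two-proportion formula,

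z = [d√n − 1.96·√(2·p̄(1−p̄))] / √(p₁(1−p₁) + p₂(1−p₂)).

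For 40% vs 50%: d√n = 0.10 × 20 = 2; 1.96 × √0.495 = 1.379; the denominator is √0.49 = 0.70. So z = 0.621/0.70 = 0.887 and power = 81.3%. It is 80.9% for 45% vs 55% and 81.3% for 50% vs 60%. The stated 81% therefore reproduces at control rates of about 39% to 51%. Exact Fisher power is 79.3% to 79.4% at control rates of 40% to 50%, 80.3% at 35% and 82.6% at 30%. The stated figure stands.

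**3. Window against wait**

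The window is 6 months and the estimated wait is about 6 months, so the slack is 6 − 6 = 0 before any delay in calling to book. The wait is approximate, so this places the typical prompted colonoscopy near the cut-off. It does not show which side.

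**4. Why no size can be given**

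Let D be the extra screening the mailing would eventually produce, s the share of it that is colonoscopy, and f the fraction of those colonoscopies done by month 6. The difference seen at 6 months from these extra tests is D × [(1 − s) + s·f]. If s = 0 or f = 1, all of D is seen; if s = 1 and f = 0, none is. The documents give neither s nor f, nor a distribution of waits from which f could be worked out. Any figure for lost power would come entirely from chosen assumptions, so none is offered.

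**5. Follow-up available**

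I count from the wave mailing, as the survey timing suggests. Neither document states when the 6 months start, which is a missing detail and no more.

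| | First wave | Last wave |
|---|---|---|
| Mailing | Sept 10, 2020 | Oct 22, 2020 |
| 6 months end | Mar 10, 2021 | Apr 22, 2021 |
| Days from mailing to SAP date (Aug 25, 2021) | 349 | 307 |
| Days from 6-month close to SAP date | 168 | 125 |
| Days from SAP date to 12 months | 16 | 58 |

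The shortest follow-up is 307 days, or about 10.1 months, so a common horizon of about 10 months existed for all 800 at the SAP date. If Aim 3's 12 months run from the June 2, 2020 extraction (an assumption), its review ends 265 days after mailing for the first wave and 223 for the last. It would then need extending.

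**The case against.** The strongest reply is that the window is a legitimate choice. The endpoint counts any screening test, and the SAP's rationale includes telling patients about home stool tests during a backlog; a 6-month window suits that route. The wait applies to both arms. The 6-month figure is an approximate planning estimate, and the documents do not give the wait in force when the mailings went out. The cumulative incidence comparison could show late divergence, and the survey item on clear screening preference partly captures choices not yet acted on, though only in the surveyed subset. All of this stands. It makes the window point a suggested improvement rather than an error. It does not remove the gap, because no horizon is stated for the cumulative incidence comparison and no count of pending procedures is planned.

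On Table 1, the reply is that the entry reads naturally as an inclusion criterion and may simply sit in the wrong column, possibly even through PDF extraction. That is likely, but the rule as printed still contradicts the Aim 2 text.

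A reader might infer that the wrong patients were enrolled. The documents do not support this: the SAP's account of the extracted list fits the intended population. A reader might also infer that the uptake comparison is biased, or that the trial was underpowered. Neither follows. The Fisher test is valid for screening by 6 months, and the 81% reproduces at plausible control rates.

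**Conclusion.** Table 1 is wrong as written and should be corrected. The contradiction rests on the text alone, needs no assumption, and has no demonstrated effect on who was enrolled.

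The window is a design choice with a possible cost in sensitivity. The size of that cost cannot be derived from the documents and may be small: if the control rates that reproduce 81% were the ones expected, many controls were expected to be screened by 6 months anyway. The conclusion rests on the protocol's own estimate of about 6 months still holding roughly at mailing, and on at least some of the intervention's effect coming through colonoscopy. A longer by-arm look would make a null result easier to interpret, but would not settle it.

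**What to change.** **Table 1.** Reconcile it with the Aim 2 text and the waitlist definition, either by moving the entry to the Eligible column or by removing its negative. Cost: one line.

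**Window.** Keep the 6-month Fisher test as the main analysis. Add, labelled post hoc:
- a by-arm cumulative incidence comparison for all 800 patients to the longest common chart follow-up (about 10 months at the SAP date, or 12 months if charts are reviewed again), split by colonoscopy and stool test;
- the number of colonoscopies scheduled but not done at 6 months, by arm.

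Cost: a short addition to the SAP, a link from trial arm to the Aim 3 chart review, and some extra chart work, since full 12-month data fall 16 to 58 days after the SAP date.

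Downsides: the SAP is written in the past tense and the analyzing statistician was unblinded, so the result can only be supportive. A 12-month cut-off has its own difficulty: patients who chose the one-year delay sit on it, and routine rescheduling of controls could by then have narrowed a real early difference.
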